#### In the Event of Infusion Prolongation

Any assessments to be performed or samples to be collected (e.g., vital signs, PK) at the end of or following EOI will still be performed or collected beginning at the delayed EOI timepoint.

All infusion interruptions and subsequent prolongations, including modified infusion times, as well as the toxicity that necessitated them, will be clearly documented on the appropriate page of the patient's CRF.

## Appendix 7 Management of Dermatologic Adverse Events

### A. Prophylaxis for IMP-Related Dermatologic AEs

Patients receiving Sym004, futuximab, or modotuximab are to receive mandatory prophylactic treatments for acneiform rash during Cycle 1 and 2 as described ([Table 17](#)).

Table 17: Mandatory Premedications for Dermatologic AEs				
Treatment	Dose	Start	Stop	Alternatives
Systemic Therapy				
minocycline or doxycycline	1 × 100 mg/day 2 × 100 mg/day	C1D1	EOC2 b	In case of intolerance 
 
• first generation cephalosporin
 
• amoxicillin
 
• erythromycin
 
• limecycline
 

Topical Therapy				
low potency steroid creams such as: 
 
• alclometasone 0.05%
 
• desonide 0.05%
 
• fluocinolone 0.01%
 
	2 × daily on face and chest	C1D1	EOC2	
moisturizer (creams or ointments)	3 × daily to the hands, and after hand washing c ; 2 × daily on the rest of the body	C1D1	Continue	

Abbreviations (in alphabetical order): C1D1, Cycle 1 Day 1; EOC2, end of Cycle 2; mg, milligram

- a. If infection is suspected (yellow crusts, purulent discharge, painful skin / nares), obtain culture and change to oral antibiotic based on sensitivities.
- b. May be continued beyond EOC2 at the Investigator's discretion or in the event of CTCAE Grade 2 rash.
- c. Use fragrance free soap.

### B. Grading and Management of IMP-Related Dermatologic AEs

The incidence and severity of dermatologic AEs observed in studies of Sym004 are discussed (Section 2.4.1). Recommendations for management of Grade 1 to Grade 3 dermatologic AEs are provided below (Table 18-Table 23).

If a patient experiences any Grade 4 dermatologic AE, the patient must be withdrawn from IMP treatment. It is strongly recommended that a dermatologist is consulted in the event of Grade 3 or Grade 4 dermatologic AE.

Table 18: Management of Rash – Sym004, Futuximab, or Modotuximab			
CTCAE Grade	Action with IMP	Treatment- Rash	
1	Papules and/or pustules covering <10% BSA, which may or may not be associated with symptoms of pruritus or tenderness	Continue at the same dose	
Topical: Face and Chest                      Steroid creams of low potency; alclometasone 0.05% or desonide 0.05% or fluocinolone 0.01%; 2×daily
 
Topical: Rest-of-body moisturizers; 2×daily
 
Systemic:                      minocycline 100 mg/day or doxycycline 200 mg/day; for at least 4 weeks

2	Papules and/or pustules covering 10-30% BSA, which may or may not be associated with symptoms of pruritus or tenderness; associated with psychosocial impact; limited instrumental ADL	Continue at the same dose  If locally debilitating for the patient, consider following guidelines for dose-delay and dose-reduction as outlined in Table 24 and Table 25	
Topical: See Grade 1
 
Systemic:
 
 
• minocycline 100 mg/day or doxycycline 200 mg/day; for at least 4 weeks
 
• 1 week course of oral steroid: methylprednisolone 4 mg tablets:                             
 
○ Day 1: 2-1-1-2
 
○ Day 2: 1-1-1-2
 
○ Day 3: 1-1-1-1
 
○ Day 4: 1-1-1
 
○ Day 5 1-0-1
 
○ Day 6: 1
 
 
 

3	Papules and/or pustules covering >30% BSA, which may or may not be associated with symptoms of pruritus or tenderness; limiting self-care ADL; associated with local superinfection with oral antibiotics indicated	Delay dose of Sym004, continue skin treatment and re-assess. Refer to Table 24 and Table 25 for further guidelines on dose-reduction	
Topical:                      See Grade 1
 
Systemic:                      See Grade 2

Abbreviations (in alphabetical order): ADL, activities of daily living; BSA, body surface area; CTCAE, Common Terminology Criteria for Adverse Events v5

1. Alternatives in case of intolerance: First generation cephalosporins, amoxicillin, erythromycin or limecycline.

If infection is suspected (yellow crusts, purulent discharge, painful skin/nares): Obtain culture and change to oral antibiotic based on sensitivity

Table 19: Management of Xerosis – Sym004, Futuximab, or Modotuximab			
	CTCAE Grade	Action with IMP	Treatment-Xerosis
1	<10% BSA and no associated erythema or pruritus	Continue at the same dose	Topical : Face moisturizing cream or ointment  ; 2×daily and Topical : Body ammonium lactate 6-12% cream; 2×daily
2	10-30% BSA associated with erythema or pruritus; limited instrumental ADL	Continue at the same dose  If locally debilitating for the patient, consider following guidelines for dose-delay and dose-reduction as outlined in Table 24 and Table 25	Topical : Face moisturizing cream or ointment  ; 2×daily and Topical : Body ammonium lactate 12% cream or salicylic acid 3-6% cream or urea 10-20% cream; 2×daily
3	>30% BSA associated with pruritus; limited self-care ADL	Delay dose of Sym004, continue skin treatment and re-assess. Refer to Table 24 and Table 25 for further guidelines on dose-reduction	Topical : Face moisturizing cream or ointment  ; 2×daily and Topical : Body ammonium lactate 12% cream or salicylic acid 3-6% cream or urea 10-20% cream; 2×daily and Topical : Eczematous areas topical steroid (e.g., triamcinolone acetonide 0.025% or desonide 0.05% or alclometasone 0.05% or fluticasone propionate 0.05%); 2×daily

Abbreviations (in alphabetical order): ADL, activities of daily living; BSA, body surface area; CTCAE, Common Terminology Criteria for Adverse Events v5

1. If prescription is not available, recommendation by pharmacist/dermatologist is acceptable

Table 20: Management of Paronychia – Sym004, Futuximab, or Modotuximab			
CTCAE Grade		Action with IMP	Treatment-Paronychia
1	Nail fold edema or erythema; disruption of the cuticle	Continue at the same dose	Topical: antibiotics (e.g., clindamycin 1% or erythromycin 1%) and vinegar soaks (i.e., soaking fingers or toes in a 1:1 solution of white vinegar in water for 15 min daily)
2	Localized intervention indicated; oral intervention indicated (e.g., antibiotic, antifungal, antiviral); nail fold edema or erythema with pain; associated with discharge or nail plate separation; limiting instrumental ADL	Continue at the same dose  If locally debilitating for the patient, consider following guidelines for dose-delay and dose-reduction as outlined in Table 24 and Table 25	Same as for Grade 1 and Topical: silver nitrate application weekly (needs consultation with dermatologist or surgeon) and Systemic: bacterial culture, oral antibiotic if infection confirmed
3	Surgical intervention or IV antibiotics indicated; limiting self-care ADL	Delay dose of Sym004, continue skin treatment and re-assess. Refer to Table 24 and Table 25 for further guidelines on dose-reduction	Same as for Grade 1 and Topical: silver nitrate application weekly (needs consultation with dermatologist or surgeon) and consider nail avulsion (needs consultation with dermatologist or surgeon) and Systemic: bacterial culture, oral antibiotic if infection confirmed

Abbreviations (in alphabetical order): ADL, activities of daily living; IV, intravenous; CTCAE, Common Terminology Criteria for Adverse Events v5

Table 21: Management of Pruritus – Sym004, Futuximab, or Modotuximab			
	CTCAE Grade	Action with IMP	Treatment-Pruritus
1	Mild or localized; topical intervention indicated	Continue at the same dose	Topical: steroid (e.g., triamcinolone acetonide 0.025%, desonide 0.05%, alclometasone 0.05%, Fluticasone propionate 0.05%); 2×daily or anti-pruritics (e.g., pramoxine 1%, doxepin 5% cream); 2×daily
2	Intense or widespread; intermittent; skin changes from scratching (e.g., edema, papulation, excoriations, lichenification, oozing/crusts); oral intervention indicated; limiting instrumental ADL	Continue at the same dose  If locally debilitating for the patient, consider following guidelines for dose-delay and dose-reduction as outlined in Table 24 and Table 25	Same as for Grade 1 and Systemic: oral antihistamines (diphenhydramine 25-50 mg; hydroxyzine 25 mg; fexofenadine 60 mg; 3×daily
3	Intense or widespread; constant; limiting self-care, ADL or sleep; oral corticosteroid or immunosuppressive therapy indicated	Delay dose of Sym004, continue skin treatment and re-assess. Refer to Table 24 and Table 25 for further guidelines on dose-reduction	Same as for Grade 2

Abbreviations (in alphabetical order): ADL, activities of daily living; CTCAE, Common Terminology Criteria for Adverse Events v5

Table 22: Management of Photosensitivity – Sym004, Futuximab, or Modotuximab			
CTCAE Grade		Action with IMP	Treatment-Photosensitivity
1	Painless erythema and erythema covering <10% BSA	Continue at the same dose	Topical: broad spectrum sunscreen with an SPF of at least 15; reapplied every 2 hours or more frequently if swimming or perspiring  and Systemic: bacterial culture, oral antibiotic if infection confirmed
2	Tender erythema covering 10-30% BSA	Continue at the same dose  If locally debilitating for the patient, consider following guidelines for dose-delay and dose-reduction as outlined in Table 24 and Table 25	Same as for Grade 1  and Topical: corticosteroids (e.g., triamcinolone acetonide 0.025% or desonide 0.05% or alclometasone 0.05% cream or fluticasone propionate 0.05%); 2×daily
3	Erythema covering >30% BSA and erythema with blistering; photosensitivity; oral corticosteroid therapy indicated; pain control indicated (e.g., narcotics or NSAIDs)	Delay dose of Sym004, continue skin treatment and re-assess. Refer to Table 24 and Table 25 for further guidelines on dose-reduction	Same as Grade 2

Abbreviations (in alphabetical order): BSA, body surface area; CTCAE, Common Terminology Criteria for Adverse Events v5; NSAID, nonsteroidal anti-inflammatory drug; SPF, sun protection factor

Table 23: Management of Fissures – Sym004, Futuximab, or Modotuximab			
Treatment Step		Action with IMP	Treatment-Fissures
1	Initiated at first occurrence	No action	Topical: 
 
thick moisturizers of zinc oxide (13-40%) cream
 
liquid glues of cyanoacrylate to seal cracks
 

2	If no improvement after 2 weeks from initiation of Step 1	No action	Topical: 
 
thick moisturizers of zinc oxide (13-40%) cream under occlusion at night
 
salicylic acid 6% cream or ammonium lactate/lactic acid 12%
 

3	If no improvement after 2 weeks from initiation of Step 2	Delay dose of Sym004 and re-assess. Discuss need for dose-reduction and/or further dose omissions with Sponsor or designee	Continue local treatment as described in Step 2

Prophylaxis for fissures includes careful use of moisturizing creams and/or ointments 3 times a day and after handwashing, using only fragrance-free soaps. Should fissures begin to form, a stepwise approach outlined above should be followed.

If fissures occur which are unresponsive to intensive therapeutic treatment as specified above, Sym004, futuximab, or modotuximab dosing should be delayed. The need for dose-reduction and/or continued dose-delays should be discussed with the Sponsor or designee, if adequate improvement is not seen after the initial dose-delay.

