#### **4.3.2 Drugs and Other Treatments to be Excluded**

*(Patients must not be receiving any of the following)*

1. Prior treatment with TAS-102 or regorafenib
2. Any antineoplastic agent for the primary malignancy (standard or investigational) without delayed toxicity within 4 weeks prior to first administration of IMP and during study, with the exception of:
  - a. Nitrosoureas and mitomycin C within 6 weeks prior to first administration of IMP and during study

Note: Patients may have received and failed prior therapy with immune modulators (e.g., PD-1, PD-L1 inhibitors) and be considered eligible for this trial.

3. Any other investigational treatments within 4 weeks prior to and during study; includes participation in any medical device or other therapeutic intervention clinical trials
4. Radiotherapy:
  - a. For lesions to be used as target lesions, within 4 weeks prior to first administration of IMP unless disease progression has been documented in the lesion post-radiotherapy, and during study
  - b. For non-target lesions, within 1 week prior to first administration of IMP

Note: Palliative (limited-field) radiotherapy for management of pain associated with bone metastases present at baseline is permitted during study. Patients with suspected new bone lesions requiring pain management should be treated and evaluated for potential disease progression.

5. Immunosuppressive or systemic hormonal therapy (> 10 mg daily prednisone equivalent) within 2 weeks prior to first administration of IMP and during study. *The following therapies are allowed:*
- a. Hormonal therapy for appetite stimulation (e.g., Megace)
  - b. Nasal, ophthalmic, inhaled, and topical glucocorticoid preparations
  - c. Hormone replacement therapy at standard doses for end-organ failure
  - d. Stable hormonal therapy for ovarian suppression for non-malignant conditions, hormonal contraceptive therapy, or post-menopausal HRT\*
  - e. Steroid therapy for contrast reaction prophylaxis
  - f. Low-dose maintenance steroid therapy for other conditions (e.g., asthma exacerbation)
  - g. Intra-articular steroid injections
  - h. Higher dose steroid therapy for treatment of an acute intercurrent illness in patients with SD or an ongoing OR. In such situations, IMP treatment should be interrupted for the duration of immunosuppressive therapy.

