### 6.9 Concurrent Treatments and Supportive Care

Therapy for other ongoing medical conditions, as well as palliative and supportive care for the underlying malignancy will be provided prior to and during this trial, as clinically indicated, and in accordance with the standard practices of the institution, except as stipulated by study eligibility criteria (**Section 4.3.2**).

Other therapies allowed during the conduct of this trial include:

1. Prophylaxis for IRRs, Dermatologic AEs, and Other IMP-Related AEs: Premedications for IRRs are mandatory throughout the study. Premedications for dermatologic AEs are mandatory during Cycles 1 and 2, and as indicated thereafter based on the occurrence of related AEs. Premedication for other patient-specific IMP-related reactions may be implemented as indicated at the Investigator's discretion.
2. Treatment of AEs or Concurrent Diseases: Instructions for management of hypomagnesemia are provided ([Appendix 8](#)). Clinical judgment should be used in the treatment of any other treatment-related AEs or concurrent diseases/conditions that require management during the study and follow-up period.
3. Blood Products and Growth Factors: Blood products and hematopoietic growth factor use is allowed, as clinically indicated.
4. Radiotherapy: Radiotherapy for pain control against non-target lesions, provided it does not substantially influence bone marrow function is allowed.
5. Bisphosphonates and denosumab: Bisphosphonates and denosumab for bone metastases and other skeletal conditions are allowed, provided the patient is on a stable dose for at least 2 months prior to study start and remains on the stable dose while receiving study treatment.
6. Immunosuppressive or systemic hormonal therapy not exceeding 10 mg daily prednisone equivalent is allowed, see [Section 4.3.2](#) for additional details.

Information on all concomitant therapies administered, as well as other interventions or procedures occurring during the trial period, must be recorded on the appropriate page of the patient's CRF.

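### The oral steroid course that Table 18 recommends for Grade 2 rash, with IMP continued, exceeds the on-study limit of 10 mg/day prednisone equivalent on four of its six days, and neither Section 4.3.2 nor Section 6.9 exempts it.

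*Protocol*

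**What the plan says.** **Appendix 7, Table 18.** For Grade 2 rash the IMP action is "Continue at the same dose". Delay or reduction is only to be considered if the rash is locally debilitating. The systemic treatment includes a "1 week course of oral steroid: methylprednisolone 4 mg tablets", with a tablet count set out for each of six days. Grade 3 rash takes the same systemic treatment by reference to Grade 2, but there the IMP dose is delayed.

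**Section 4.3.2, item 5.** The excluded treatments include "Immunosuppressive or systemic hormonal therapy (> 10 mg daily prednisone equivalent) within 2 weeks prior to first administration of IMP and during study". Eight allowed therapies follow, a to h. None is oral steroid treatment of an IMP-related rash. The only entry for higher-dose treatment of an illness is 5h: "Higher dose steroid therapy for treatment of an acute intercurrent illness in patients with SD or an ongoing OR". It carries a condition: "In such situations, IMP treatment should be interrupted for the duration of immunosuppressive therapy".

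**Section 6.9.** Item 1 lists prophylactic premedication among the allowed therapies. Item 2 covers treatment of adverse events: "Clinical judgment should be used in the treatment of any other treatment-related AEs". Item 6 states: "Immunosuppressive or systemic hormonal therapy not exceeding 10 mg daily prednisone equivalent is allowed", and refers to Section 4.3.2 for detail.

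**The concern.** Two rules that are both in force meet in the same patient. A site treating Grade 2 rash as Table 18 recommends gives an oral steroid dose that Sections 4.3.2 and 6.9, read literally, do not permit on study. Nothing says which takes precedence. Nothing says either whether the only higher-dose treatment entry, with its requirement to interrupt IMP, is meant to reach a rash for which Table 18 continues IMP.

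The situation is foreseeable. Table 1 reports treatment-related acneiform rash in 57.6% and rash in 31.6% of Sym004 patients. These are all-grade figures, and the protocol gives no Grade 2 incidence. Section 6.7.1 expects patients with adequately controlled Grade 2 rash to go on to further cycles. Amendment 5 suspends neither Appendix 7 nor Section 4.3.2, and both enrolled patients may continue Sym004. At stake are consistent handling of a common event and consistent recording of protocol deviations.

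**Working it through.** **Inputs.** Tablet strength 4 mg and tablets per day from Table 18; limit of 10 mg/day prednisone equivalent from Sections 4.3.2 and 6.9. The methylprednisolone-to-prednisone ratio is not in the protocol. I assume a range of 1.0 (mg for mg) to 1.25.

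**Formula.** Daily methylprednisolone = tablets × 4 mg. Prednisone equivalent = daily methylprednisolone × ratio. Break-even ratio = 10 ÷ daily methylprednisolone; the limit is exceeded for any ratio above it.

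| Day | Tablets | Methylprednisolone (mg) | Equivalent at 1.0 (mg) | Equivalent at 1.25 (mg) | Break-even ratio | Above 10 mg? |
|---|---|---|---|---|---|---|
| 1 | 2+1+1+2 = 6 | 24 | 24 | 30 | 0.42 | yes |
| 2 | 1+1+1+2 = 5 | 20 | 20 | 25 | 0.50 | yes |
| 3 | 1+1+1+1 = 4 | 16 | 16 | 20 | 0.63 | yes |
| 4 | 1+1+1 = 3 | 12 | 12 | 15 | 0.83 | yes |
| 5 | 1+0+1 = 2 | 8 | 8 | 10 | 1.25 | no |
| 6 | 1 | 4 | 4 | 5 | 2.50 | no |

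Total: 24 + 20 + 16 + 12 + 8 + 4 = 84 mg, or 84 ÷ 6 = 14 mg/day on average. The Day 1 peak is 24 ÷ 10 = 2.4 to 30 ÷ 10 = 3.0 times the limit. The count of four days is the same across the assumed range. At 1.25, Day 5 reaches 10 mg exactly and does not exceed it.

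**Passages side by side.**

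- Section 4.3.2 item 5 applies during the study, so the limit is not only an entry criterion.
- Entries a to g cover appetite stimulation, local preparations, replacement and other stable hormonal therapy, contrast prophylaxis, low-dose maintenance and joint injections. None is this course.
- Entry h allows higher doses but is limited to acute intercurrent illness in patients with SD or an ongoing OR. If rash is outside h, the course has no exemption. If rash is taken to be inside h, IMP is to be interrupted, which is the opposite of Table 18 at Grade 2, and a patient not yet assessed as SD or OR would still not qualify.
- Section 6.9 item 2 permits treatment of adverse events by judgment but sets no steroid dose and states no exemption. Item 6 of the same list restates the limit.

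At Grade 3 the limit is exceeded in the same way, but IMP is already delayed, so the question of continuing IMP during the course arises only at Grade 2.

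**The case against.** The best defence is that the limit cannot be meant for steroids that the protocol itself directs. Section 8.1.1.2 and Appendix 6 require a glucocorticoid before every infusion, at a recommended equivalent of 80-100 mg IV methylprednisolone, and that too is missing from entries a to h. Read literally, Section 4.3.2 would bar every infusion. Appendix 7 is the specific rule for rash, and Sections 6.5.4.8, 8.1.2 and 11.3 send sites to it. Section 6.9 item 2 also allows treatment of adverse events.

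This shows what the authors may have intended, but it does not settle the text. Premedication is expressly allowed in Section 6.9 item 1. The rash course has no corresponding line, and item 2 is silent on the limit that item 6 repeats. An exemption has to be inferred.

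It is also fair that Table 18 gives recommendations, so a site could omit the steroid course and satisfy both passages. That avoids a deviation only by not following the recommended management.

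Several stronger readings are tempting but not supported:

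- *Section 6.9 exempts premedication only, or places all supportive care under Section 4.3.2.* Item 2 separately allows treatment of adverse events. The opening reference to Section 4.3.2 concerns other medical conditions and supportive care for the malignancy.
- *Section 6.9 ties higher doses to interruption of IMP.* That condition stands in 4.3.2 item 5h alone and is written for intercurrent illness; Section 6.9 only cross-refers. On a strict reading the rash course is barred outright, and stopping IMP would not make it permitted.
- *Section 9.1 forces discontinuation.* Its item on physician decision is discretionary and names a non-permitted medication only as an example.
- *24 mg is the daily dose.* It is the Day 1 peak of a taper.
- *Dose intensity is an affected outcome.* Section 16.5.3 belongs to the full analysis that Amendment 5 drops.

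**Conclusion.** The conflict is real but limited. The Table 18 course exceeds the 10 mg/day limit on Days 1 to 4 of 6, with a peak of 24 to 30 mg prednisone equivalent, and no passage exempts it. The only outside assumption is the conversion ratio (1.0 to 1.25). The four-day result would fail only at a ratio of 0.83 or below, or above 1.25, when Day 5 would exceed the limit too.

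The practical effect is on rash management and deviation recording for the two remaining patients, whose data Section 16.5 presents as profiles or listings. No efficacy result or planned comparison is affected. It should be corrected, but it does not threaten the trial's conclusions. The documents do not show which passage states the intended clinical rule, and this review takes no position on it.

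**What to change.** Reconcile Table 18 (systemic treatment at Grades 2 and 3, and the IMP action at Grade 2) with Section 4.3.2 items 5 and 5h and Section 6.9 items 2 and 6. One consistent statement, cross-referenced in all three places, should say whether the rash steroid course falls under the 10 mg/day limit and whether the interruption condition in 5h applies to it. The sponsor's medical team makes that choice. The cost is one cross-referenced sentence by amendment, with no added procedures or data collection.

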
AE Management
	
Dose Delay AEs that do not meet the protocol discontinuation criteria, but nevertheless warrant dose modification, may be managed by temporary dose delay to allow for amelioration of the toxicity.
 
Dose Reduction In the event of Grade 3 treatment-related AEs that are self-limiting or can be managed by supportive care or other therapy, the patient may continue in the study if there is evidence of response, disease stabilization, or other clinical benefit, but must do so at a reduced dose of IMP. Patients may not be retreated until retreatment criteria are met. Once a patient has undergone dose reduction for any reason, the patient will continue to be treated at the reduced dose throughout the remainder of their time on study treatment.

Infusion-Related Reactions
	
Instructions for the grading and management of IRRs are provided. In all cases the Investigator should use best clinical judgment in managing such reactions.
 
 
• For Grade 3 reactions, the infusion will be STOPPED. The patient will be either discontinued from treatment or must receive subsequent treatments at a reduced dose and at a prolonged infusion rate.
 
• For Grade 4 reactions, the infusion will be STOPPED and the patient will be permanently discontinued from treatment.
 

Dermatologic Toxicity
	
Patients will be monitored weekly for evidence of dermatologic AEs.
 
Dose delay and/or inpatient dose-reduction(s) will be required upon occurrence of Grade 3 AEs, and may be implemented in the event of a Grade 2 dermatologic reaction that is debilitating for the patient.
 
Recommendations for management of Grade 1 to 3 dermatologic AEs are provided. Patients must be withdrawn from IMP treatment in the event of a Grade 4 dermatologic AE.

Hypomagnesemia, Hypocalcemia, and Hypokalemia
	
Patients will be monitored weekly for hypomagnesemia, hypocalcemia, and hypokalemia. In the event of Grade 3-4 hypomagnesemia, repletion is required as well as predosing electrocardiograms (ECGs) to monitor for QTc prolongation. For Grade 4 hypomagnesemia that is refractory to IV magnesium-replacement therapy, dosing with Sym004 should be delayed or reduced. Full management instructions are provided in the protocol.

SAFETY MONITORING
	

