**C. Dose Reduction Guidelines for IMP-Related Dermatologic AEs**

Dose delay and/or inpatient dose-reduction(s) will be required upon occurrence of Grade 3 anti-EGFR-associated dermatologic AE, and should be implemented according to the following tables (**Table 24**, **Table 25**):

Table 24: Dose Reduction for Grade 3 Dermatologic AEs - Sym004			
Dermatologic AE Grade 3	Immediate Action	Outcome Improvement	Sym004
First occurrence	Delay dose	Grade ≤1	Continue at same dose
		Grade 2	Reduce to 4.5 mg/kg
		No improvement	Discontinue
Second occurrence	Delay dose	Grade ≤1	Continue at same dose
		Grade 2	At dose of 6.0 mg/kg: Reduce to 4.5 mg/kg At dose of 4.5 mg/kg: Reduce to 3.0 mg
		No improvement	Discontinue
Third occurrence	Delay dose	Grade ≤1	Continue at same dose
		Grade 2	At dose of 6.0 mg/kg: Reduce to 4.5 mg/kg At dose of 4.5 mg/kg: Reduce to 3.0 mg/kg At dose of 3.0 mg/kg: Discontinue
		No improvement	Discontinue
Fourth occurrence	Discontinue	Any	Discontinue

Abbreviations (in alphabetical order): kg, kilogram; mg, milligram

Note: Dose reductions for 9 mg/kg loading NA. For dose delays, re-assess after ≤ 2 weeks. Longer delays are allowed if no recovery to < Grade 2 after 2 weeks

Table 25: Dose Reduction for Grade 3 Dermatologic AEs - Futuximab or Modotuximab			
Dermatologic AE Grade 3	Immediate Action	Outcome Improvement	Futuximab or Modotuximab
First occurrence	Delay dose	Grade ≤1	Continue at same dose
		Grade 2	Reduce to 1.5 mg/kg
		No improvement	Discontinue
Second occurrence	Delay dose	Grade ≤1	Continue at same dose
		Grade 2	At dose of 3.0 mg/kg: Reduce to 1.5 mg/kg At dose of 1.5 mg/kg: Discontinue
		No improvement	Discontinue

Abbreviations (in alphabetical order): kg, kilogram; mg, milligram

Note: Dose reductions for 9 mg/kg loading NA. For dose delays, re-assess after ≤ 2 weeks. Longer delays are allowed if no recovery to < Grade 2 after 2 weeks

In each case, the next treatment should be delayed, and the patient’s condition should be re-assessed after 1-2 weeks. Treatment should be delayed further if the AE remains at Grade 3 after 2 weeks.

In the case of a Grade 2 dermatologic AE which is locally debilitating for the patient, the guidelines outlined above may be followed at the Investigator’s discretion.

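### Table 23 allows unchanged dosing through the first four weeks of a fissure at any grade, while four other places in the protocol require delay or reduction, or bar retreatment, at Grade 3

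*Protocol*

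**What the plan says.** Appendix 7 section B presents Tables 18 to 23 as management recommendations for dermatologic events of Grade 1 to Grade 3. Tables 18 to 22 set the dosing action by CTCAE grade. Their Grade 3 rows read "Delay dose of Sym004, continue skin treatment and re-assess" and refer the reader to Tables 24 and 25.

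Table 23 (fissures) is organised by treatment step and names no grade. In its column for action with the study drug:

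- Step 1 starts at first occurrence and calls for no dosing action.
- Step 2 starts after 2 weeks without improvement on Step 1 and again calls for no dosing action.
- Step 3 is the first point at which dosing is delayed. Its trigger is "If no improvement after 2 weeks from initiation of Step 2". Dose reduction is then a matter to discuss with the sponsor.

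The text below the table sets no grade limit: "Should fissures begin to form, a stepwise approach outlined above should be followed". It continues: "If fissures occur which are unresponsive to intensive therapeutic treatment as specified above, Sym004, futuximab, or modotuximab dosing should be delayed".

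Four other places set a rule for Grade 3:

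- **Appendix 7 section C:** "Dose delay and/or inpatient dose-reduction(s) will be required upon occurrence of Grade 3 anti-EGFR-associated dermatologic AE". Table 24 gives a delay as the immediate action, and the text under Table 25 says "In each case, the next treatment should be delayed".
- **Synopsis:** the Dermatologic Toxicity row says "Dose delay and/or inpatient dose-reduction(s) will be required upon occurrence of Grade 3 AEs". The AE Management row requires a reduced dose after a Grade 3 treatment-related event and says patients may not "be retreated until retreatment criteria are met".
- **Sections 8.2.3 and 9.1:** both allow continuation after a Grade 3 treatment-related event only at a reduced dose, with no retreatment until the Section 6.7.1 criteria are met.

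**The concern.** A site facing a fissure will look in the fissure table. There it finds no dosing action for the first four weeks, whatever the severity, and a delay that depends on failed local treatment rather than on grade. If the fissure is Grade 3, the same protocol elsewhere requires dosing to be held or reduced. Both instructions cannot be followed.

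The conflict extends to dose reduction, which Table 23 leaves to discussion and Sections 8.2.3 and 9.1 make mandatory.

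The text is in force. Amendment 5 withdrew the efficacy and specialty assessments but left the drug doses and toxicity management in place, and Section 6.7.3 lets both enrolled patients continue on Sym004. What is at stake is the safety handling of those two patients. No efficacy analysis, error rate or sample size is involved.

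**Working it through.** The plan gives no figure to reproduce. The check is a comparison of rules, with a small calculation of timing and frequency.

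**1. Does a Grade 3 fissure fall under both rules?** Yes. Section B places Table 23 among the tables covering Grade 1 to Grade 3. Section 10.2.1 requires every adverse event to be graded, using the general Grade 1 to 5 definitions where CTCAE has no specific scale. Table 1 in Section 2.4.1 reports skin fissures with a Grade 3 or higher share. A step-based table therefore does not take fissures outside the Grade 3 rules. Grade 4 is not affected: Appendix 7 requires withdrawal.

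**2. Time to first delay.** Under Table 23, Step 1 is day 0, Step 2 is day 14 and Step 3 is day 14 + 14 = 28. Under section C the next dose is delayed, and dosing is weekly (Section 6.5.4.6).

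**3. Doses allowed while the fissure is Grade 3.**

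- Protocol read as a whole, fissure related to study drug: 0. Sections 8.2.3 and 9.1 and the synopsis bar retreatment until the Section 6.7.1 criteria are met, and Section 8.2.3 applies within cycles as well as between them.
- Table 23 read alone, keeping only the Section 6.7.1 check before a new cycle, with doses on Days 1, 8, 15 and 22 and Sym004 at 6 mg/kg. The count depends on the visit at which the fissure is noted, and the next Day 1 is blocked:
  - Day 8: 3 doses, 3 × 6 = 18 mg/kg
  - Day 15: 2 doses, 2 × 6 = 12 mg/kg
  - Day 22: 1 dose, 6 mg/kg
  - Day 1: 0 doses

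The second set describes a misreading, not exposure that the protocol permits.

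**4. How often this could arise.** Table 1 gives skin fissures as 20.0% (3.0%), the bracket being the Grade 3 or higher percentage. It can be read in two ways. With n = 2 patients, expected cases are n × p and the chance of at least one is 1 − (1 − p)².

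- Bracket as a share of patients, p = 0.030: expected 2 × 0.030 = 0.06; chance 1 − 0.97² = 0.059.
- Bracket as a share of fissure reactions, p = 0.20 × 0.030 = 0.006: expected 2 × 0.006 = 0.012; chance 1 − 0.994² = 0.012.

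Table 1 pools Sym004 studies with weekly doses up to 12 mg/kg, so these rates may not match the 9/6 mg/kg regimen.

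**The case against.** The strongest reply is that the wording already ranks the rules. Section B offers recommendations, section C states a requirement, and the requirement covers Grade 3 skin events as a class. The two also work on different axes: Table 23 escalates local care by persistence, while section C acts on severity. On that view the no-action entry means only that the local treatment step triggers no dose change, and Step 3 adds a delay for fissures that persist below Grade 3. This reading is sensible and an experienced investigator may well adopt it. But the protocol does not state it. Table 23 is the event-specific instruction, and its entry stands in the column for action with the study drug.

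The second reply is that nothing will go wrong in practice. Most of this stands. Section C follows directly after the table, the skin is examined weekly (Section 7.2.6), Appendix 7 strongly recommends a dermatologist at Grade 3, and only two patients are treated. These points limit the consequence but do not remove the contradiction.

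A third reply is that the change is not free, because Section 13.4.1 routes protocol changes through a formal amendment. That is correct.

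Finally, Table 24 and Section 8.2.3 disagree on the dose at restart after recovery to Grade 1 or less (same dose against reduced dose). That is a separate and broader discrepancy, affecting all Grade 3 dermatologic events.

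**Conclusion.** The concern holds. Table 23 as written gives a dosing instruction for a Grade 3 fissure that conflicts with Appendix 7 section C, the synopsis, Section 8.2.3 and Section 9.1. Followed alone, it postpones the first delay to day 28, where the other rules hold or reduce dosing once Grade 3 is reached.

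The size is small. The expected number of affected cases in the two treated patients is 0.012 to 0.06, assuming the pooled Table 1 rates apply to this regimen. An actual dosing error would require a site to overlook all four other rules. The zero-dose result for the protocol as a whole assumes the fissure is judged related to study drug. What remains is a contradictory instruction in a safety table that is still in use, and it should be corrected.

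**What to change.** Add one line to Table 23: the no-action entries at Steps 1 and 2 apply to Grade 1-2 fissures only; a Grade 3 fissure requires dose delay from first occurrence under Tables 24/25 and Section 8.2.3, with no retreatment until the Section 6.7.1 criteria are met, while the local treatment steps continue alongside. This gives fissures the Grade 3 delay and cross-reference that Tables 18 to 22 already carry.

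The cost is that line and the minor amendment needed to issue it. Visits, assessments and data collection do not change. The line does not settle the restart dose after recovery, which needs its own correction for all dermatologic events.
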